9.5.5. Appropriateness of Safety Assessments

Safety evaluations selected for this study are typical of those for this subject/patient population and utilize widely accepted measures.

10. ADVERSE EVENTS

An AE is defined as any untoward medical occurrence in a subject administered a pharmaceutical product during the course of a clinical investigation. An AE can therefore be any unfavorable and unintended sign, symptom, or disease temporally associated with the use of an investigational product, whether or not thought to be related to the investigational product. Any worsening of the patient's disease under study or other medical conditions will also be considered to be an adverse event, unless it is within the normal range of disease fluctuation for that patient.

An unanticipated adverse device effect (UADE) is any serious adverse effect on health or safety or any life-threatening problem or death caused by, or associated with, a device, if that effect problem, or death was not previously identified in nature, severity, or degree of incidence in the investigational plan, or any other unanticipated serious problem associated with a device that relates to the rights, safety, or welfare of subjects.

Subjects will be monitored throughout the study for AEs, from administration of the first dose of VFI through the follow-up phone call/EOS visit. Adverse events that are identified at the last assessment visit (or the early termination visit) as specified in the protocol must be recorded on the AE CRF with the status of the AE noted. All events that are ongoing at this time will be recorded as ongoing on the CRF. All (both serious and nonserious) AEs must be followed until they are resolved or stabilized, or until attempts to determine resolution of the event are exhausted. The investigator should use his/her discretion in ordering additional tests as necessary to monitor the resolution of such events.

The procedures specified in [Section 10.4](#) are to be followed for reporting SAEs.

10.1. Recording Adverse Events

Adverse events are to be recorded on the AE page of the CRF. The following information will be recorded:

- Assessment of whether or not the AE is an SAE ([Section 10.2.1](#))
- Assessment of AE intensity ([Section 10.2.2](#))
- Assessment of AE relationship to study product ([Section 10.2.3](#))
- Action taken - categorized as none, study drug discontinued, dose modified, required concomitant medication, required procedure, or other.
- Outcome - recorded as event resolved, resolved with sequelae, ongoing, or death.

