Table 2. Performance Sampling Schedule – (Two Performance Periods)					
Nominal Time Relative to Start of VFI Bolus Injection	FD001 and FD003 Plasma Sample	Iohexol Plasma Sample	Volume of Blood drawn^b	Timed Urine Collection	
Predose (within 30 minutes)	X	X	6 mL	Pool urine from patient arrival to departure.	
0 minutes	VFI and Iohexol Administration				
15 minutes	X	X	7 mL		
60 minutes	X	X	7 mL		
80 minutes	X		4 mL		
120 minutes	X	X	7 mL		
180 minutes	X	X	7 mL		
Dialysis Treatment (4 hours)					
Pre- Rinseback	X		4 mL		
Equilibrium time Post-Dialysis (1 hour)					
Predose (within 5 minutes of drug administration)	X	X	7 mL		
0 minutes	VFI and Iohexol Administration ^a				
15 minutes	X	X	7 mL		
60 minutes	X	X	7 mL		
80 minutes	X		4 mL		
120 minutes	X	X	7mL		
180 minutes	X	X	7 mL		

Blood Samples will be drawn at approximately the times listed in Table 2.2; however due to the nature of the study some variation in timing may occur. Regardless of the time and number of blood draws, no subject will have more than 80 mLs blood drawn for this study within a 24-hour period.
 
Abbreviations: FD001 = 5 kD carboxymethyl dextran; FD003 = 150 kD carboxymethyl dextran; VFI = visible fluorescent injectate.
 
^{a.} Second VFI and iohexol administration will occur approximately 8 hours after the initial administrations.
 
^{b.} Each blood draw will be taken as follows: 1 mL waste draw, 3mL FAST blood sample, 3 mL Iohexol Sample Note: Blood samples will be collected from the venous side of the arteriovenous fistula/graft. Performance blood samples will be collected as close to the nominal time point as possible. The allowable window for postdose blood sample collection relative to the start of VFI/iohexol bolus injection will be ±5 minute.
					

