8.4. Measurements of Compliance

Study product and comparator will be administered by qualified healthcare professionals at the study site as designated by the investigator. Details regarding dosing, including the dose administered and the date and time of dosing, will be recorded.

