8.7. Concomitant Medications and Other Restrictions

8.7.1. Concomitant Medications

Maintenance medications as prescribed by their physicians are permitted. All medications (prescription and OTC), vitamin and mineral supplements, and herbs taken during the study will be documented on the concomitant medication case report form (CRF). Information recorded will include: start and stop dates and times, dose and route of administration, and indication. Medications taken for a procedure should also be included.

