10.2.3. Relationship to Study Product

The relationship of an AE to the study product should be determined by the investigator according to the following criteria:

- Not related: The event is most likely produced by other factors such as the subject's clinical condition, intercurrent illness, or concomitant drugs, and does not follow a known response pattern to the study product, or the temporal relationship of the event to study product administration makes a causal relationship unlikely
- Possibly related: The event follows a reasonable temporal sequence from the time of drug administration, and/or follows a known response pattern to the study product, but could have been produced by other factors such as the subject's clinical condition, intercurrent illness, or concomitant drugs
- Related: The event follows a reasonable temporal sequence from the time of drug administration, and/or follows a known response pattern to the study product, and cannot be reasonably explained by other factors such as the subject's clinical condition, intercurrent illness, or concomitant drugs

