11.4. Safety Analysis

The number and percentage of subjects reporting any TEAE will be tabulated by system organ class, preferred term (coded using Medical Dictionary for Regulatory Activities), and cohort. Treatment-emergent AEs will be further classified by severity and relationship to study product.

Vital signs and clinical laboratory test data (observed and change from baseline) will be summarized by cohort and time point using appropriate descriptive statistics. Physical examination findings will only be listed.

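### Adverse events are rated for relationship to VFI only and tabulated by a one-level cohort, so the record does not show whether iohexol or dialysis was suspected and the table cannot compare Dose 1 with Dose 2

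*Protocol*

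**What the plan says.** Section 10.1 opens the AE record with "Adverse events are to be recorded on the AE page of the CRF. The following information will be recorded". Five items follow: seriousness, intensity, relationship, action taken and outcome. The relationship item reads "Assessment of AE relationship to study product", and section 10.2.3 repeats that object: "The relationship of an AE to the study product should be determined by the investigator according to the following criteria".

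Study product here means VFI. Table 4 lists VFI under that label and iohexol under a separate comparator label. Section 8.4 keeps them apart too: "Study product and comparator will be administered by qualified healthcare professionals at the study site as designated by the investigator".

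In Table 2 the 0-minute row of both performance periods is "VFI and Iohexol Administration". A 4-hour dialysis and a 1-hour equilibration lie between the two periods.

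For the analysis, section 11.4 says: "The number and percentage of subjects reporting any TEAE will be tabulated by system organ class, preferred term". The remaining splitting variable in that sentence is cohort, and the events are then classified by severity and by relationship to study product. Section 8.3 places all patients in a single cohort. Section 10 monitors AEs from the first VFI dose to the follow-up call, which Table 1 puts at Day 31.

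**The concern.** VFI safety and tolerability is the third primary objective, and section 4.6.2 says that dialysis patients have not received VFI before. Each patient gets two VFI injections, two iohexol injections and a dialysis session on one day. Sections 4.3 and 4.6.2 name acute anaphylactic reaction to dextran products as the main worry. Exclusion criterion 9 recognizes low blood pressure on dialysis as something these patients experience.

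Two questions therefore follow for any Day 1 event: which exposure was suspected, and did the event come after the first or the second dose? The relationship scale gives an answer for VFI alone, and the event table has no time dimension. At stake is how clearly the small safety data set can be read. No inferential claim is affected, since the trial is unpowered and safety reporting is descriptive.

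**Working it through.** The protocol gives no error rate, power or sample size figure on this point. The check compares sections and adds up one timeline.

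**1. What the relationship scale does with a co-injected agent (10.2.3).**
- The top category requires that other factors, including concomitant drugs, cannot reasonably explain the event.
- The middle category covers events that fit the timing or a known pattern but could have had another cause.
- The lowest category needs other factors to be the most likely source with no known VFI pattern, or timing that makes VFI unlikely.
- Suppose an acute reaction occurs soon after minute 0 and either agent could explain it. It fits the VFI timing, and iohexol is a reasonable alternative, so it falls in the middle category. No listed field says that iohexol was the alternative.
- Suppose blood pressure falls during dialysis and the investigator judges dialysis responsible. The event can be rated not related to VFI, but no listed field names dialysis as the suspected cause.

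**2. The Day 1 timeline.**
- Table 2: 3 h of sampling after Dose 1 + 4 h dialysis + 1 h equilibration = 8 h to Dose 2. This reproduces the interval of about 8 hours in the footnotes to Tables 1 and 2.
- Sections 6.1 and 8.2 put Dose 1 about 4 h before dialysis: 4 + 4 + 1 = 9 h to Dose 2. The two descriptions differ by about an hour, which does not affect this point.
- Adding 3 h of sampling after Dose 2 gives 8 + 3 = 11 h or 9 + 3 = 12 h.
- Day 1 thus holds four successive windows: after Dose 1, dialysis, equilibration, after Dose 2. Follow-up to Day 31 is a fifth.

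**3. What the table does with those windows (11.4).**
- Cohort has one level, so splitting by it leaves one column. All five windows fall into it.
- Severity and relationship to VFI divide that column further, but neither carries dose number or time.
- The same section summarizes vital signs and laboratory data by time point, so events are the exception.

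**4. What supports an onset split.** Dosing date and time are recorded (8.4). Medication records include "start and stop dates and times" (8.7.1). The list in 10.1 names no corresponding item for AEs.

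**5. What onset time would and would not achieve.** It would place an event in one of the windows. It would not separate VFI from iohexol, because both start from the same 0-minute point at each dose.

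**The case against.** A reader might infer that events cannot be attributed to VFI at all, or that an iohexol reaction or a dialysis event is counted indistinguishably with a VFI reaction. The protocol does not support that. Section 10.2.3 makes the investigator weigh temporal sequence, clinical condition and other drugs for each event, and 11.4 reports events by the resulting category. Vital signs before and about 60, 120 and 180 minutes after each administration, summarized by time point, also give a partial view of the two doses.

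A reader might also infer from 10.1 that AE onset will not be collected. That is an argument from silence. The list also omits the event term, without which the coding in 11.4 could not be done, and treatment-emergent status presupposes an onset. The CRF page may hold more than the list. Taken alone, the unnamed onset item is only a missing detail.

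Finally, event tables by dose or interval are often left to the SAP, which is not at hand and may contain one. That stands as a reason for restraint. It does not reach the relationship rating, which is a data collection rule that the protocol fixes: an SAP cannot tabulate suspected relationship to iohexol or dialysis if nobody was asked. It also leaves 11.4 naming a splitting variable with a single level.

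**Conclusion.** The point holds as a minor one. Relationship is defined for VFI only, although a second trial-administered agent is injected at the same moment and dialysis separates the doses. The listed data therefore do not record whether iohexol or dialysis was the suspected cause. The only grouping in the planned event table is empty, so AEs after Dose 1 and Dose 2 cannot be compared from it.

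The extent is structural: four Day 1 windows over about 11 to 12 hours, plus follow-up to Day 31, in one column. I put no error figure on it. With about 10 patients one might say that each misassigned event moves a percentage by 10 points (1/10), but that is only an upper bound. Section 11.4 counts patients, so a second event in the same patient and category adds nothing, and the protocol gives no basis for a misassignment rate.

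The conclusion assumes that study product means VFI throughout sections 10 and 11, as Table 4 and section 8.4 indicate, and that no CRF or SAP outside the protocol adds the missing ratings or split.

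**What to change.** - **Section 10.2.3, with the matching item in 10.1:** rate relationship separately to VFI, to iohexol, and to dialysis or study procedures.
- **Section 11.4:** replace the split by cohort with onset interval: Dose 1 to start of dialysis, start of dialysis to Dose 2, Dose 2 to departure on Day 1, and follow-up. Define the end of the third interval explicitly, because Table 1 uses the word discharge for Day 31 while the design text uses it for the end of Day 1.
- **Section 10.1:** name AE onset and stop date and time, so that the interval table rests on a stated data item.
- **Limitation to state:** because VFI and iohexol share minute 0 at both doses, onset time cannot separate them. The separate iohexol rating records the investigator's suspicion and does not supply independent evidence.

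The cost is a few extra CRF fields and one table, with slightly more data entry at the site. No visit, sample or administration changes.

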10.2. Assessment of Adverse Events

The investigator will assess each AE for seriousness, intensity, and relationship to study product.

10.2.1.Serious Adverse Events

The investigator is responsible for determining whether an AE meets the definition of an SAE. An SAE is any AE occurring from ICF signing through the follow-up phone call/EOS visit that results in any of the following outcomes:

- Death
- A life-threatening adverse drug experience
- Inpatient hospitalization or prolongation of existing hospitalization
- A persistent or significant disability/incapacity
- A congenital anomaly/birth defect

Important medical events that may not result in death, be life-threatening, or require hospitalization may be considered an SAE when, based upon appropriate medical judgment, they may jeopardize the subject and may require medical or surgical intervention to prevent any of the outcomes listed in this definition. Examples of such medical events include allergic bronchospasm requiring intensive treatment in an emergency room or at home, blood dyscrasias or convulsions that do not result in inpatient hospitalization, or the development of drug dependency or drug abuse.

Note: SAEs require immediate reporting to the sponsor. Refer to “Reporting Serious Adverse Events” (Section 10.4) for details.

10.2.2.Intensity

The intensity of an AE will be graded according to the following definitions:

- Mild: Any symptom of which the subject is aware, but which is easily tolerated; asymptomatic or mild symptoms; clinical or diagnostic observations only; intervention not indicated.
- Moderate: Any symptom which is discomforting enough to cause interference with a subject's usual activity; minimal, local, or noninvasive intervention indicated; limiting age-appropriate instrumental activities of daily living (ADL).
- Severe: Any symptom which causes a subject's inability to perform usual activity; severe or medically significant but not immediately life-threatening; hospitalization or prolongation of hospitalization indicated; disabling; limiting self-care ADL.

It should be noted that a severe adverse event need not be serious in nature and that an SAE need not, by definition, be severe.

10.2.3. Relationship to Study Product

The relationship of an AE to the study product should be determined by the investigator according to the following criteria:

- Not related: The event is most likely produced by other factors such as the subject's clinical condition, intercurrent illness, or concomitant drugs, and does not follow a known response pattern to the study product, or the temporal relationship of the event to study product administration makes a causal relationship unlikely
- Possibly related: The event follows a reasonable temporal sequence from the time of drug administration, and/or follows a known response pattern to the study product, but could have been produced by other factors such as the subject's clinical condition, intercurrent illness, or concomitant drugs
- Related: The event follows a reasonable temporal sequence from the time of drug administration, and/or follows a known response pattern to the study product, and cannot be reasonably explained by other factors such as the subject's clinical condition, intercurrent illness, or concomitant drugs

10.3. Discontinuation due to Adverse Events

Any subject who experiences an AE may be withdrawn at any time from the study at the discretion of the investigator. Subjects withdrawn from the study due to an AE, whether serious or nonserious, may be followed by the investigator until the clinical outcome of the AE is determined. The AE(s) should be noted on the appropriate CRFs and the subject's progress should be followed until the AE is resolved or stabilized as determined by the investigator. The sponsor must be notified. If the AE relates to overdose of study treatment, the Investigator's Brochure should be consulted for details of any specific actions to be taken.

10.4. Reporting Serious Adverse Events

In the event of any SAE reported or observed during the study, whether or not attributable to the study drug, site personnel will report it immediately by telephone to the medical monitor. Any SAE attributable to study participation will be reported promptly to the IRB as required by the Richard L. Roudebush Veterans Affairs Medical Center.

10.5. Documentation and Reporting of Immediately Reportable Adverse Events

Any unexpected adverse event that could adversely affect the safety of the subjects or the conduct of the study and any serious adverse event, which occurs during the course of this study, will be reported to the sponsor immediately (ie, within 24 hours).

The information will comprise at least the following data:

- Name, address, and telephone number of the reporting investigator
- Investigational product(s)
- Study code
- Subject identification number, initials, sex, and date of birth
- Description of the adverse event, measures taken and outcome (if resolved)
- Likelihood of drug causation of the adverse event assessed by the investigator

The sponsor ensures that all relevant information about suspected serious unexpected adverse reactions that are fatal or life threatening is recorded and reported as soon as possible to the FDA, and in any case no later than 7 days after knowledge by the sponsor of such a case, and that relevant follow up information is subsequently communicated within additional 7 days. The study team will be responsible for informing the IRB of any promptly reportable events within 5 days of discovery, in accordance with IU policy.

All other suspected serious unexpected adverse reactions will be reported to the FDA as soon as possible but with a maximum of 15 days of first knowledge by the sponsor. The sponsor will inform all investigators. In accordance with IU policy, the study team will be responsible for informing the IRB of any promptly reportable events within 5 days of discovery including those listed below.

The sponsor will inform as soon as possible, but no later than 15 days after knowledge, the FDA and the IRB about any event which necessitates reconsideration of the benefit-risk-ratio of the investigational drug. These events are in particular:

- Single cases of expected serious adverse reactions with an unexpected outcome.
- An increased incidence of expected serious adverse reactions which is considered clinically relevant.
- Suspected serious unexpected adverse reactions occurring after a concerned person has completed the study.
- Events related to the conduct of the study or the development of the drugs possibly affecting the safety of the concerned persons.

All additional measures deemed necessary through new findings and taken by the sponsor or the investigator to protect the safety of the persons concerned and their triggering circumstances will be reported as soon as possible to the FDA and the IRB.

10.6. Pregnancy

The investigator must report any pregnancy to the medical monitor and to the Richard L. Roudebush Veterans Affairs Medical Center within 1 business day of becoming aware of the pregnancy. An uncomplicated pregnancy will not be considered an AE or SAE; however, all pregnancies will be followed through birth and 3 months postdelivery.

Pregnancies in the sexual partners of male subjects will be captured from the time the subject is first exposed to the investigational product until 90 days after last exposure to the investigational product.

Any congenital abnormalities in the offspring of a subject who received study drug will be reported as a SAE. The outcome of any pregnancy and the presence or absence of any congenital abnormality will be recorded in the source documentation and reported to the medical monitor and sponsor.

10.7. Drug-induced Liver Injury

Subjects will be monitored for signs of drug-induced liver injury (DILI). Study product will be withheld in the event of potential DILI.

Potential events of DILI will be defined as meeting all of the following criteria (as specified in the [FDA Guidance for Industry Drug-induced Liver Injury: Premarketing Clinical Evaluation, 2009](#)):

- Alanine aminotransferase or aspartate aminotransferase $> 3 \times$ ULN
- Total bilirubin $> 2 \times$ ULN without initial findings of cholestasis (elevated serum alkaline phosphatase)
- No other reason can be found to explain the combination of laboratory value increases (eg, acute viral hepatitis; alcoholic and autoimmune hepatitis; hepatobiliary disorders; nonalcoholic steatohepatitis; cardiovascular causes; concomitant treatments)

Potential events of DILI will be reported as SAEs ([Section 10.4](#)). All subjects with potential DILI will be closely followed until abnormalities return to normal or baseline or until all attempts to determine resolution of the event are exhausted.

